7.3. Unscheduled Visits

If, during the investigation, a subject requires an unscheduled visit to the clinical site, the following information will be collected at a minimum:

- Chief complaint prompting the visit. If the reason is an adverse event, the applicable eCRF for the adverse event must be completed and subject record completed as appropriate
- Date and time of the visit and all procedures completed at the unscheduled visit
- Review of adverse event and concomitant medications
- Documentation of any test article dispensed or collected from the subject, if applicable
- Slit lamp findings (using the Slit Lamp Classification Scale)

If the Investigator withdraws a subject from the study, the final study visit case report forms must be completed indicating the reason(s) why the subject was withdrawn. The subject record must be completed documenting the date and primary reason for withdrawal and the study CRA notified.

Any ocular and non-ocular Adverse Events that are ongoing at the time of the study visit will be followed by the Investigator, within licensure, until they have resolved, returned to pre-treatment status, stabilized, or been satisfactorily explained. If further treatment i.e., beyond licensure is required, the subject will be referred to the appropriate health care provider.

The following information will be collected during an unscheduled visit.

Unscheduled Visit		
Step	Procedure	Details
U.1	Chief Complaints	Record the subject's chief complaints for reasons for the unscheduled visit.
U.2	Adverse Events and Concomitant Medications Review	Review any changes to the subject's medical history or concomitant medications from the previous study visit. Record any changes, and any adverse events.
U.3	Entrance VA	Record the entrance distance visual acuity (OD, OS and OU) to the nearest letter.
U.4	Subjective Sphero-cylindrical Refraction	Perform bare-eye subjective sphero-cylindrical refraction with a phoropter (adopt the maximum plus to maximum visual acuity (MPMVA) approach and use the duo-chrome test for binocular balancing) and record the best corrected distance visual acuity to the nearest letter (OD, OS, and OU).
U.5	Slit Lamp Biomicroscopy	FDA Slit Lamp Classification Scale will be used to grade the findings. If the clearance of the fluorescein needs to be expedited, preservative-free rewetting drops may be instilled.

Unscheduled Visit			
Step	Procedure	Details	
U.6	Exit Visual Acuity	Record the subject's exit distance visual acuity (OD, OS, and OU) to the nearest letter.	[REDACTED] [REDACTED]

7.4. Laboratory Procedures

N/A.

8. SUBJECTS COMPLETION/WITHDRAWAL

8.1. Completion Criteria

Subjects are considered to have completed the study if they:

- provided informed consent
- they are eligible
- they complete the study procedures

8.2. Withdrawal/Discontinuation from the Study

A subject will be withdrawn from the study for any of the following reasons:

- Subject death during the study period
- Subject withdrawal of consent
- Subject not compliant to protocol
- Subject develops significant or serious adverse events causing discontinuation of treatment
- Investigator's clinical judgment regarding the subject safety reasons (that it is in the best interest of the subject to stop treatment)

For discontinued subjects, the Investigator will:

- Complete the current visit (scheduled or unscheduled)
- Complete the Final Evaluation, indicating the reason that the subject was discontinued from the study
- Collect used test article and discard them, unless otherwise stated in Section 7.2

9. PRE-STUDY AND CONCOMITANT INTERVENTION/MEDICATION

Concomitant medications will be documented during screening and updated during the study.

10. DEVIATIONS FROM THE PROTOCOL

Investigator will notify study sponsor upon identification of a protocol deviation. Major protocol deviations must be reported to the sponsor within 24 hours after discovery of the protocol deviation. The Investigator will report deviations per IRB/IEC requirements. All deviations will be tracked and corrective actions implemented as appropriate.

If it becomes necessary for the Investigator to implement a deviation to eliminate an immediate hazard to the trial subject, the Investigator may implement the deviation immediately without notification to the sponsor. Within 24 hours after the implemented deviation, the Investigator must notify and provide the rationale to the Sponsor and, as required, the IEC/IRB.

11. STUDY TERMINATION

The occurrence of one or more Unanticipated Serious Adverse Device Effect (USADE), or any SAE where the relationship to study agent cannot be ruled out, may result in stopping further dispensing of test article. In the event of a USADE or SAE, the Sponsor may unmask the treatment regimen for the subject(s) and will discuss this with the Investigator before any further subjects are enrolled.

The Sponsor will determine when a study will be stopped. The Principal Investigator always has the discretion to initiate stopping the study based on patient safety or if information indicates the study's results are compromised.

JJVC reserves the right to terminate the study at any time for any reason. Additionally, the IEC/IRB reserves the right to terminate the study if an unreasonable risk is determined. The study can be terminated by the Principal Investigator at the individual clinical site due to specific clinical observations, if in their opinion, after a discussion with JJVC, it is determined that it would be unwise to continue at the clinical site.

JJVC (and the IEC/IRB and DMC, if applicable) will evaluate all adverse events. If it is determined that an adverse event presents an unreasonable risk, the investigation, or that part of the investigation presenting the risk, will be terminated, as soon as possible.

Should the study be terminated (either prematurely or as scheduled), the Investigator will notify the IEC/IRB and Regulatory Authority as required by local regulatory requirements.

12. PROCEDURE FOR HANDLING PRODUCT QUALITY COMPLAINTS

N/A

13. ADVERSE EVENTS

13.1. Definitions and Classifications

Adverse Event (AE) – An AE is “any untoward medical occurrence, unintended disease or injury, or untoward clinical signs (including abnormal laboratory findings) in subjects, users or other persons, whether or not related to the investigational medical device.

Note 1 to entry: This definition includes events related to the investigational medical device or the comparator.

Note 2 to entry: This definition includes events related to the procedures involved.

Note 3 to entry: For users or other persons, this definition is restricted to events related to investigational medical devices.”¹

An AE includes any condition (including a pre-existing condition) that:

1. Was not present prior to the study, but appeared or reappeared following initiation of the study
2. Was present prior to the study, but worsened during the study. This would include any condition resulting from concomitant illnesses, reactions to concomitant medications, or progression of disease states
3. Pregnancy must be documented as an adverse event and must be reported to the clinical monitor and to the Sponsor immediately upon learning of the event

Serious Adverse Event (SAE) – An SAE is any untoward medical occurrence that:

- Results in death
- Is life threatening
- Requires in-patient hospitalization or prolongation of existing hospitalization
- Results in persistent or significant disability/incapacity (e.g., a sight threatening event, a significant persistent or permanent change, impairment, damage, or disruption to the subject's body)
- Is a congenital anomaly/birth defect, or?
- Requires intervention to prevent permanent damage (the use of the test article resulting in a condition which requires medical or surgical intervention to preclude permanent impairment of the body structure or a body function). Important medical events that may not result in death, be life-threatening, or require hospitalization may be considered an SAE when, based upon appropriate medical judgment, they may jeopardize the patient or subject and may require medical or surgical intervention to prevent one of the outcomes listed in the above definition

Diagnoses and conditions that are considered Ocular Serious Adverse Events include, but not limited to:

- Microbial Keratitis (MK)
- Iritis (including cells in the anterior chamber)
- Permanent decrease in best spectacle corrected visual acuity equivalent to 2 acuity lines or greater
- Central Corneal Opacity
- Central Corneal Neovascularization
- Uveitis
- Endophthalmitis
- Hypopyon
- Hyphemia
- Penetration of Bowman's Membrane
- Persistent Epithelial Defect
- Limbal cell Damage leading to Conjunctivization

Significant Adverse Events – Those events that are usually symptomatic and warrant discontinuation (temporary or permanent) of the test article (excluding Serious Adverse Events).

Diagnoses and conditions that are considered Ocular Significant Adverse Events include, but not limited to the following:

- Significant Infiltrative Events (SIE)
- Superior Epithelial Arcuate Lesions (SEALs)
- Any Temporary Loss of > 2 Lines of BSCVA
- Other grade 3 or higher corneal findings, such as abrasions or edema
- Non-contact lens related corneal events - e.g. Epidemic Keratoconjunctivitis (EKC)
- Asymptomatic Corneal Scar
- Any corneal event which necessitates temporary lens discontinuation > 2 weeks

Non-Significant Adverse Events – Those conditions that are usually asymptomatic and usually do not warrant discontinuation (temporary or permanent) of the test article. However, the Investigator may choose to treat as a precautionary measure.

Diagnoses and conditions that are considered Ocular Non-Significant Adverse Events include, but not limited to the following:

- Non-significant Infiltrative Event (NSIE)
- Superficial Punctate Keratitis (SPK)
- Conjunctivitis: Bacterial, Viral, Allergic
- Blepharitis
- Meibomianitis
- Contact Dermatitis
- Localized Allergic Reactions
- Any corneal event not explicitly defined as serious or significant adverse event, which necessitates temporary lens discontinuation < 2 weeks

Adverse Device Effect (ADE) – An ADE is an “adverse event related to the use of an investigational medical device.

Note 1 to entry: This definition includes adverse events resulting from insufficient or inadequate instructions for use, deployment, implantation, installation, or operation, or any malfunction of the investigational medical device.

Note 2 to entry: This definition includes any event resulting from use error or from intentional misuse of the investigational medical device.”¹

Unanticipated Adverse Device Effect (UADE) – Any serious adverse effect on health or safety or any life-threatening problem or death caused by, or associated with, the test article, if that effect, problem, or death was not previously identified in nature, severity, or degree of incidence in the investigational plan, Investigator’s Brochure or protocol, or any other unanticipated serious problem associated with the test article that relates to the rights, safety and welfare of subjects.

13.2. Assessing Adverse Events

In conjunction with the medical monitor, the Investigator will evaluate adverse events to ensure the events are categorized correctly. Elements of categorization will include:

- Seriousness/Classifications (see definition in Section 13.1)
- Causality or Relatedness – i.e. the relationship between the test article, study treatment or study procedures and the adverse event (not related; unlikely related; possibly related; related - see definition in Section 13.2.1)
- Adverse Event Severity – Adverse event severity is used to assess the degree of intensity of the adverse event (mild; moderate; severe for all events - see definition in Section 0)
- Outcome – not recovered or not resolved; recovering or resolving; recovered or resolved with sequelae; recovered or resolved; death related to adverse event; unknown
- Actions Taken – none; temporarily discontinued; permanently discontinued; other

13.2.1. Causality Assessment

Causality Assessment – A determination of the relationship between an adverse event and the test article. The test article relationship for each adverse event should be determined by the investigator using these explanations:

- Not Related- An adverse event that is not related to the use of the test article, study treatment or study procedures
- Unlikely Related – An adverse event for which an alternative explanation is more likely, e.g. concomitant treatment, concomitant disease(s), or the relationship of time suggests that a causal relationship is not likely
- Possibly Related – An adverse event that might be due to the use of the test article, or to the study treatment or study procedures. An alternative explanation, e.g. concomitant treatment, concomitant disease(s), is inconclusive. The relationship in time is reasonable. Therefore, the causal relationship cannot be excluded
- Related – An adverse event that is listed as a possible adverse effect (device) or adverse reaction (drug) and cannot be reasonably explained by an alternative explanation, e.g. concomitant treatment of concomitant disease(s). The relationship in time is very suggestive, e.g. it is confirmed by de-challenge and re-challenge

13.2.2. Severity Assessment

Severity Assessment – A qualitative assessment of the degree of intensity of an adverse event as determined by the Investigator or reported to him/her by the subject. The assessment of severity is made irrespective of test article, study treatment or study procedure relationship or seriousness of the event and should be evaluated according to the following scale:

- Mild – Event is noticeable to the subject, but is easily tolerated and does not interfere with the subject's daily activities
- Moderate – Event is bothersome, possible requiring additional therapy, and may interfere with the subject's daily activities
- Severe – Event is intolerable, necessitates additional therapy or alteration of therapy and interferes with the subject's daily activities

13.3. Documentation and Follow-Up of Adverse Events

The recording and documenting of adverse events (ocular and non-ocular) begins when the subjects are exposed to the test article, study treatment or study procedure. Adverse events reported before the use of test article, start of study treatment, or study procedures will be

recorded as medical history. However, if the condition deteriorates at any time during the study it will be recorded and reported as an AE. Untoward medical events reported after the subject's exit from the study will be recorded as adverse events at the discretion of the Investigator.

Upon finding an adverse event, the Principal Investigator will document the condition in the subject record and in the eCRFs. He/she will complete the Adverse Event /eCRF.

Complete descriptions of all adverse events must be available in the subject record. All Adverse Events including local and systemic reactions not meeting the criteria for "serious adverse events" shall be captured on the appropriate case report form or electronic data system. All adverse events occurring while the subject is enrolled in the study must be documented appropriately regardless of relationship.

It is the Investigator's responsibility to maintain documentation of each reported adverse event. All adverse events will be followed in accordance with applicable licensing requirements. Such documentation will include the following:

- Adverse event (diagnosis not symptom)
- Drawings or photographs (where appropriate) that detail the finding (e.g., size, location, and depth, etc.)
- Date the clinical site was notified
- Date and time of onset
- Date and time of resolution
- Adverse event classification, severity, and relationship to test articles, as applicable
- Treatment regimen instituted, including concomitant medications prescribed, in accordance with applicable licensing requirements
- Any referral to another health care provider if needed
- Outcome, ocular damage (if any)
- Likely etiology
- Best corrected visual acuity at the discovery of the event and upon conclusion of the event

In addition, if an infiltrate(s) is present, he/she will complete the Corneal Infiltrate Assessment eCRF. Where necessary, a culture of the corneal lesion will be collected to determine if the infection is microbial in nature. If cultures are collected, the date of culture collection and laboratory utilized will be recorded.

Changes in the severity of an AE shall be documented to allow an assessment of the duration of the event at each level of intensity to be performed. Adverse events characterized as intermittent require documentation of the onset and duration of each episode. Changes in the assessment of relationship to the Test Article shall also be clearly documented.

Subjects who present with an adverse event shall be followed by the Investigator, within licensure, until all signs and symptoms have returned to pre-treatment status, stabilized, or been satisfactorily resolved. If further treatment beyond licensure is required, the patient will be referred to the appropriate health care provider. The Investigator will use his/her clinical judgment as to whether a subject reporting with an adverse event will continue in the study. If

a subject is discontinued from the study, it will be the responsibility of the Investigator to record the reason for discontinuation. The Investigator will also document the adverse event appropriately and complete the Adverse Event eCRF. Any subjects with ongoing adverse events related to the test article, study treatment or study procedures, as of the final study visit date, should be followed to resolution of the adverse event or until referral to an appropriate health care provider, as recommended by the Investigator. Non-ocular adverse events that are not related to the test article, study treatment, or study procedures may be recorded as "ongoing" without further follow-up.

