4.3. Enrollment Target and Study Duration

The target enrollment is 20 subjects, with a minimum of 12 subjects completing the 1-visit study, which will last for approximately 2.5 hours.

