1.20	Corneal Topography	Perform post-treatment corneal topography with the Oculus Keratograph	SOP_C12_Oculus_Keratograph_V2
1.21	Non-Invasive Tear Break Up Time (NITBUT)	Perform post-treatment NITBUT using Oculus Keratograph 5 (OD, OS)	SOP_C12_Oculus_Keratograph_V2
1.22	Eyelid Photography	The upper and lower eyelid margins of the subject will be photographed, OD, OS	Work Aid: Eyelid Photography

FINAL EVALUATION

The final evaluation will ordinarily take place immediately following the last scheduled follow-up visit per the study protocol. It may also take place at any point the subject discontinues the study or is terminated from the study.

Final Evaluation			
Step	Procedure	Details	
F.1	Final Exam Form	Indicate if the subject completed the study successfully. If subject discontinued from the study, indicate the reason.	
F.2	Exit Slit Lamp Biomicroscopy (White Light)	FDA Slit Lamp Classification Scale will be used to grade the findings and determine eligibility. Note: If the white light appearance of the cornea reveals significant findings, use NaFl to evaluate.	
F.3	Snellen Exit Acuity	Record the corrected distance visual acuity to the nearest letter (OD, OS, and OU).	

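### Section 13.3 leaves recording of events reported after exit to the investigator's choice, although exit ordinarily ends a single visit of about 2.5 hours and Section 7.3 makes the form compulsory

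*Combined protocol and SAP*

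**What the plan says.** Section 13.3 starts adverse event recording at first exposure to the test article, treatment or a study procedure. It requires documentation of every event that occurs during enrollment, related or not. Events reported after a subject's "exit from the study will be recorded as adverse events at the discretion of the Investigator".

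Section 4.3 sets a "minimum of 12 subjects completing the 1-visit study, which will last for approximately 2.5 hours". Table 3 shows one visit only. Section 7.2 states: "The final evaluation will ordinarily take place immediately following the last scheduled follow-up visit per the study protocol".

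Section 7.3 opens with the condition "If, during the investigation, a subject requires an unscheduled visit to the clinical site" and lists what is then collected. On the chief complaint it says: "If the reason is an adverse event, the applicable eCRF for the adverse event must be completed and subject record completed as appropriate".

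Section 13.4.1 requires notice to the sponsor within 24 hours for serious and significant events in the *study period*, a term the protocol does not define for the individual subject. Section 5.2 states that subjects, investigators and site staff are all unmasked.

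**The concern.** In a study with several visits, discretion after exit affects only a short tail of follow-up. Here there is no follow-up: exit comes on the day of treatment and no later contact is scheduled. An eyelid or corneal event that a subject first notices that evening or the next day therefore falls under the optional rule, however serious and however plausibly related.

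Three things are at stake. The safety tables could show no events partly because recording was optional, and a reader of the report could not tell. The choice rests with someone who knows which eye received which device, so recording could differ between devices. And two sections give the site different instructions for the same subject, so similar events may be handled differently.

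**Working it through.** No formula in the plan bears on this point, so the check sets the sections side by side.

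**1. When the compulsory window closes.** The protocol does not define exit. I take it to be the Final Evaluation, because steps F.2 and F.3 are the exit examinations. The visit of about 2.5 hours also contains consent, screening and baseline measurements, all before any heat is applied. The compulsory window after first treatment is therefore shorter than 2.5 hours.

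**2. Where an unscheduled visit falls.** Step U.2 reviews changes since the previous study visit. With one scheduled visit, that is Visit 1. For a subject who completes it, an unscheduled visit normally comes after exit.

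**3. Two readings of Section 7.3.** Its trigger is a visit *during the investigation*, which is not defined.

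| Reading of 7.3 | Adverse event prompts a visit after exit | Event reported after exit without a visit |
|---|---|---|
| Covers visits until the study closes | Form compulsory under 7.3, optional under 13.3: conflict | Optional under 13.3 |
| Covers only subjects not yet exited | Optional under 13.3 | Optional under 13.3 |

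The first reading gives a conflict. The second removes it, but leaves 7.3 with almost nothing to do for completers and widens the optional area. Neither settles what must be recorded.

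**4. Duties that survive exit.**

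| Section | Duty | Cut-off at exit? |
|---|---|---|
| 13.4 | Notify the sponsor within 24 hours of discovery (serious or significant) or 2 days (non-significant) | None stated |
| 13.4.1, UADE | Report within 24 hours of learning of the effect | None stated |
| 13.4.1, serious or significant | Notify within 24 hours, for events in the *study period* | Unclear: the subject's visit, or the study of about 1.5 months in the synopsis |
| 11 | Possible halt on a USADE, or on an SAE whose relationship cannot be ruled out | None stated; not tied to the eCRF |
| 13.3 | Follow related events ongoing at the final visit | Continues, but only for events already present |

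Expedited notice therefore does not stop at exit. What 13.3 makes optional is the adverse event record on which the safety summaries of Section 14.1 rest.

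**5. Can the share of serious events affected be computed?** Section 13.1 lists 12 ocular serious events. Three of them (3/12 = 25%) imply by their wording a course longer than one visit: "Permanent decrease in best spectacle corrected visual acuity equivalent to 2 acuity lines or greater", persistent epithelial defect, and limbal cell damage leading to conjunctivization. Those words describe how long an event lasts, not when it starts. No onset times are given, so the share first reported after exit could be anything from none to all 12.

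**6. Weight of one event.** With 12 completers, one subject is 1/12 = 8.3%. With 20 enrolled, one subject is 1/20 = 5.0%.

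**7. Calendar time to study end.** The synopsis gives about 1.5 months including 1 month of enrollment, leaving 1.5 − 1 = 0.5 month. If all of it follows enrollment, each subject has 0.5 to 1.5 months between exit and study end (about 15 to 45 days at 30 days per month). If all of it precedes enrollment, the range is 0 to 1 month. The synopsis does not say which.

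**The case against.** The case against is substantial, and much of it stands.

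- **Most serious events would be lost.** A reader might infer this from the lists in Section 13.1. It needs onset times that the documents do not give. An event that begins during the visit must be documented, and if related and ongoing it is followed under 13.3 and can be classified later.
- **The two-week limit shows how short the window is.** A reader might set the item "Any corneal event which necessitates temporary lens discontinuation > 2 weeks" against the visit length. That item is on the significant list, not the serious list. It measures how long lens wear is interrupted, and Appendix B confirms that no study lenses are worn. The comparison shows nothing about detection.
- **The 24-hour notice and the termination rule would be disabled.** A reader might infer this too. Sections 11 and 13.4 turn on occurrence and discovery, the UADE duty turns on the investigator learning of the effect, and none is tied to the form.
- **Sections 7.3 and 13.3 may govern different subjects.** This is possible, because 7.3 also deals with withdrawals. Step U.2 and the single-visit schedule make it the less natural reading, and it leaves the optional rule untouched.
- **The risk is low.** Both products are marketed and used once, and Section 1.5 describes the procedural risks as self-limiting. This bears on how often the rule would matter, not on whether it is sound.
- **The medical monitor shares in categorization (Section 13.2).** That safeguard applies to adverse events being evaluated. It does not say which reports after exit must be recorded.

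What remains is the discretion itself, its lack of exceptions, the overlap with 7.3, and the undefined *study period*.

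**Conclusion.** The concern holds in a limited form. Section 13.3 allows a serious, ocular or possibly related event first reported after exit to go unrecorded as an adverse event, at the choice of an unmasked investigator, in a study whose only visit lasts about 2.5 hours. It conflicts with 7.3 on the natural reading of that section and sits unclearly with 13.4.1.

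The effect is on the completeness of the recorded safety data. One event is worth 5.0 to 8.3 percentage points of the crude subject-level rate, but the documents give no basis for predicting how many would be missed. The conclusion assumes that exit means the Final Evaluation and that it takes place on the day of treatment, as Section 7.2 ordinarily expects. It does not extend to the primary temperature analysis.

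**What to change.** In Section 13.3, replace the discretionary sentence with a rule such as: *Any serious event, any ocular or eyelid event, and any other event possibly related to test article or procedures that is reported to the site after exit and before study end will be recorded on the Adverse Event eCRF and classified under Sections 13.1 and 13.2.*

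Then:

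- state in Section 7.3 that its recording duty runs to the same date, and that reports received without a visit are covered by 13.3;
- define *study period* in Section 13.4.1 to end on that date for every subject;
- give study end as a stated date or event, because the synopsis does not show how much time the last subject would have.

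The cost is protocol wording and a few more adverse event forms. The reported event rate may look slightly less favourable. No extra visit, subject or change to treatment is needed.
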